7.1 Participant Discontinuation/Withdrawal from the Study

The participants are allowed to withdraw from the study at any point with no penalty.

7.2 Lost to Follow-Up

Not applicable.

8 - Statistical Considerations

8.1 Statistical Hypotheses

In Aim 1, we will test the working hypotheses that 1) food security will improve (i.e. food security score will decrease) among participants visiting a food pantry that transition to online ordering in the follow-up period, but not among those in the control arm, and 2) participants visiting a food pantry that transitions to online ordering will also select more fruits and vegetables per visit, have higher fruit and vegetable intake, and spend less time accessing food pantries in the follow-up (vs. baseline) period compared to those in the control arm.

For Aim 2, we hypothesize that improvements in food security due to online ordering will be larger for younger adults.

8.2 Sample Size Considerations

To calculate our sample size, we used estimates from a similar study that found that a food bank-delivered intervention (diabetes-appropriate food packages, text-based health education, and referrals to health care) resulted in a decrease in the mean food security score from 2.8 to 2.3, or a 6.3% decrease in the percentage of participants with low or very low food security status.⁴⁰ Based on this study, we assume the standard deviation of the food security score is 1.5 and estimate that 155 participants in each condition (total n=310) will provide 90% power to detect a 0.5 difference in food security score between experimental and control conditions. To account for a potential attrition rate of 20% in the follow-up period, we plan to recruit a total sample size of 193 participants per condition (total n=386).

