3.1 Primary Objective

Our primary objectives are to determine whether the transition to online ordering at a choice-based food pantry network influences food security status among low-income adults and determining whether there are differences in impact by age group.

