8.4 Statistical Analyses

We will perform a linear regression to assess balance of demographic characteristics between conditions; because of the natural experiment design, these characteristics should be balanced. To assess differences in outcomes between study conditions, we will regress the outcome variable on indicator variables for the experimental conditions, with the control condition as the reference group; if necessary, we will also adjust for any respondent characteristics that may be unbalanced by condition. The design and methods proposed will achieve robust and unbiased results because random assignment to an intervention group or control group in the context of a natural experiment minimizes bias.

We will also test for potential interaction effects at the individual-level by adding an interaction term for age group (18-61 vs. ≥ 62 years). In the food pantry network, an average of 25% of clients served are above 61 years of age, so we will have adequate variation to assess potential interactions by age group. For assessing differences in the frequency of food pantry visits per month at the food pantry-level, we will also add an interaction term for age group, which the

food pantry network measures as child (<18 years), adult (18-61 years), and older adult (≥ 62 years).

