8.4.2 Analysis of the Primary Efficacy Endpoint(s)

The primary outcome for Aim 1 is food security status. We will use the United States Department of Agriculture (USDA) six-item food security survey module to assess food security status, where the range of points is zero to six points, and higher points corresponds to lower food security.⁴¹ Food security status will be categorized according to USDA guidelines, including very low (5-6); low (2-4); and high or marginal (0-1) food security. We will perform a linear regression to assess balance of demographic characteristics between conditions; because of the natural experiment design, these characteristics should be balanced. To assess differences in outcomes between study conditions, we will regress the outcome variable on indicator variables for the experimental conditions, with the control condition as the reference group; if necessary, we will also adjust for any respondent characteristics that may be unbalanced by condition.

The primary outcome for Aim 2 is the same as Aim 1 and measured using the same specifications. We will test for potential interaction effects at the individual-level by adding an interaction term for age group (18-61 vs. ≥ 62 years). In the food pantry network, an average of 25% of clients served are above 61 years of age, so we will have adequate variation to assess potential interactions by age group.

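### Section 8.2 claims 90% power without stating alpha or sidedness: 155 per condition delivers it at one-sided 5% (or two-sided 10%), but gives about 83% at two-sided 5%.

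*Combined protocol and SAP*

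**What the plan says.** Section 8.2 takes an SD of 1.5 and a difference of 0.5 points from a similar food bank study. On that basis the authors "estimate that 155 participants in each condition (total n=310) will provide 90% power to detect a 0.5 difference in food security score". Recruitment is then raised to 193 per condition: "To account for a potential attrition rate of 20% in the follow-up period".

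No alpha, sidedness, p-value threshold or confidence level appears there, in the hypotheses (8.1), or anywhere in the analysis sections (8.4 to 8.4.8).

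The wording elsewhere points both ways:

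- Section 8.1 is directional: "food security will improve (i.e. food security score will decrease) among participants visiting a food pantry that transition to online ordering". It does not declare a one-sided test.
- Section 3.1 is neutral. The aim is to "determine whether the transition to online ordering at a choice-based food pantry network influences food security status among low-income adults".
- Section 8.4.2 is also neutral, opening its analysis with "To assess differences in outcomes between study conditions".
- The model in 8.4 is a regression on condition: "we will regress the outcome variable on indicator variables for the experimental conditions, with the control condition as the reference group". Covariates enter only if respondent characteristics turn out to be unbalanced. Adjustment for the baseline food security score is not named.

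**The concern.** A power figure has meaning only for a stated test. Here the reader must infer the test from the sample size, and the inferred test (one-sided 5% or two-sided 10%) is more lenient than the two-sided 5% that most readers will assume.

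Two things are at stake:

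- **The risk of a missed effect.** If two-sided 5% is used, that risk is larger than 8.2 implies.
- **The primary verdict.** Because the choice is open, an analyst could defend either test after seeing the data, and a band of results is significant under one and not the other. If one-sided 5% is used, the false-positive rate in the favourable direction is 5% rather than 2.5%, and readers are not told.

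**Working it through.** **Inputs from 8.2:** difference 0.5; SD 1.5; power 90%; 155 per condition, equal groups; attrition 20%; 193 recruited per condition. **Assumed:** alpha and sidedness (each case shown), independent observations, no covariate adjustment.

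**1. Reproducing 155.** The normal formula is n per condition = 2 × (z_α + z_β)² × SD² / difference². Here 2 × 1.5² / 0.5² = 18, and z_β = 1.2816 for 90% power.

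- One-sided 5% or two-sided 10%: 18 × (1.6449 + 1.2816)² = 154.1, so 155. The t-test calculation gives 154.8, also 155.
- Two-sided 5% or one-sided 2.5%: 18 × (1.9600 + 1.2816)² = 189.1, so 190. The t-test calculation gives 190.1, so 191.

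The plan's figure matches the first case exactly.

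**2. Power at 155 per condition** (noncentral t, 308 degrees of freedom).

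| Test | Power | Chance of missing a true 0.5 |
|---|---|---|
| One-sided 5% | 90.0% | 10.0% |
| Two-sided 10% | 90.0% | 10.0% |
| Two-sided 5% | 83.3% | 16.7% |

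**3. Where the verdict changes.** The standard error of the difference is 1.5 × √(2/155) = 0.1704. The smallest significant observed improvement is:

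- one-sided 5% or two-sided 10%: 1.650 × 0.1704 = 0.281;
- two-sided 5%: 1.968 × 0.1704 = 0.335.

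An observed improvement between these two values passes one test and fails the other. If the true effect is 0.5, the chance of landing there is 90.0 − 83.3 = 6.7 percentage points.

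**4. What 155 supports at two-sided 5%.** Power of 90% is reached for a difference of about 0.55 points (0.554 by the t-test, 0.552 by the normal formula), or for 0.5 points if the SD is about 1.35 or less. For 0.5 points, power is 88.0% at SD 1.4 and 78.3% at SD 1.6; these alternative SDs are assumptions.

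**5. Room for attrition at two-sided 5%.** With 193 recruited and 191 needed, the margin is (193 − 191)/193 = 1.0%, against the 20% allowed for. With no attrition, power at 193 per condition is 90.4%.

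**6. Adjusting for the baseline score.** With residual SD = 1.5 × √(1 − r²), where r is the baseline to follow-up correlation, two-sided 5% power at 155 per condition is 86.6% at r = 0.3, 92.2% at r = 0.5 and 95.5% at r = 0.6. The documents give no correlation, so these values are assumptions.

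**The case against.** The strongest reply is that nothing in 8.2 is miscalculated. The 155 is correct for a one-sided 5% test, 8.1 states its hypotheses directionally, and neutral wording in an objective does not commit anyone to a two-sided test. On this view one clause is missing, and the 83% rests on a level that the documents never adopt. It stands that 155 is not an arithmetic error and that the 83% is conditional. But a predicted direction is not a declared one-sided test, and the 90% remains tied to no stated test.

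A second reply is that two-sided 5% could also yield about 155 if the analysis gained precision from baseline data: a correlation of about 0.42 to 0.43 with baseline adjustment, or about 0.59 with change scores. That is possible. However, no correlation is given, adjustment for the baseline score is not specified, and the unadjusted one-sided calculation matches exactly without further assumptions.

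Third, the consequence is moderate. The disputed band carries about a 7% chance when the true effect is 0.5, and attrition may be below 20%: at 10% attrition (about 174 per condition) two-sided power would be about 87%. This is fair, but 8.2 itself plans for 155 analysed.

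Finally, all these figures assume independent observations, while 4.1 and 5.5 describe one intervention pantry and one control pantry. Site differences could matter more than the gap between 90% and 83%. That is a separate limitation, and it does not supply the missing alpha.

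**Conclusion.** The concern holds. Alpha and sidedness are not stated, and the 90% power in 8.2 is correct only for a one-sided 5% or two-sided 10% test. If the primary comparison is tested at two-sided 5%, power at the planned 155 per condition is about 83%, a shortfall of about 7 percentage points. The same sample then gives 90% power for about 0.55 points rather than 0.5.

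These figures rest on the plan's SD of 1.5, independent observations and no covariate adjustment; two-sided 5% is an assumed convention, not document text. The defect is a power claim without a declared test, and it leaves the decision rule for the primary outcome open. The study can proceed, but the rule should be fixed before results are seen.

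**What to change.** Before analysis, state alpha and sidedness in both 8.2 and 8.4.2, and make the power statement match.

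- **If the test is two-sided 5%:** restate 8.2 to say that 155 per condition gives about 83% power for a 0.5-point difference (unadjusted, SD 1.5, independent observations), or 90% power for about 0.55 points.
- **If one-sided 5% was intended:** declare it in both sections, link it to the directional hypothesis in 8.1, and justify it on grounds other than keeping the 90% figure.

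As an option, pre-specify adjustment for the baseline food security score, which is already collected, instead of adjusting only for characteristics found to be unbalanced. If this is done, report two-sided 5% power over a range of assumed correlations (about 87%, 92% and 96% at r = 0.3, 0.5 and 0.6).

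The cost is wording in 8.2 and 8.4.2, with no extra participants or data; the optional adjustment would also need a matching line in 8.4. The downside is a less favourable stated power, or having to defend a one-sided test.

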5.4 Lifestyle Considerations

Participants in the intervention arm will have to transition with their food pantry to online ordering after the baseline data collection period regardless of their participation in this research study. The change will be brought on “naturally” by the food pantry (not the NYULH researchers or specifically as part of this research study). There will be no other restrictions during any other parts of the study pertaining to lifestyle and/or diet.

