8.3 Populations for Analyses

The study population is a sample of adults aged ≥ 18 years.

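### Loss to follow-up is set aside in 7.2 although 8.2 allows for 20% attrition, and the stated regression gives no rule for missing follow-up scores and does not use baseline scores

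*Combined protocol and SAP*

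**What the plan says.** - **Section 8.2** states that "155 participants in each condition (total n=310) will provide 90% power"; the target is half a point between the two arms. It then raises 155 to 193 per condition (386 in total) "To account for a potential attrition rate of 20% in the follow-up period".
- **Section 7.2**, headed "7.2 Lost to Follow-Up", consists of the words "Not applicable".
- **Section 8.3** describes the analysis population in one sentence: "The study population is a sample of adults aged ≥ 18 years". It does not say whether people without a follow-up score are included.
- **Sections 8.4, 8.4.2 and 8.4.8** specify a linear regression of the outcome on study condition, adjusted if necessary for respondent characteristics that differ between conditions. None mentions missing outcomes, a comparison of lost with retained participants, or a sensitivity analysis.
- **Section 8.1** states the hypothesis as a change: the score falls at the pantry that moves online and does not fall at the control pantry.
- **Sections 5.5, 6.1 and 10.3** describe retention: contact details taken at baseline, an appointment card, email or text reminders, pantry handouts and a $50 follow-up payment. **Section 9.6** plans unique IDs that allow survey responses to be linked.

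**The concern.** Sections 7.2 and 8.2 cannot both stand. The mismatch matters because the analysis text does not fill the gap. Without a rule, ordinary regression software drops anyone lacking the outcome, so the primary result becomes a comparison of follow-up respondents at two pantries. Recruiting 193 instead of 155 restores precision only. It does nothing about bias if the people lost differ from those kept, and differ in a way that is not the same in the two arms.

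Unequal loss is plausible here because the arms do not go through the same experience. Section 5.4 says: "Participants in the intervention arm will have to transition with their food pantry to online ordering after the baseline data collection period". Some reminders are handed out through the pantry (Section 5.5), so they miss people who have stopped attending. Nothing in the documents says that such people will still be called.

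The stated model also has no baseline or period term. The score already collected at baseline, which is the best available information on those lost, is therefore left out. That fits poorly with a hypothesis about change.

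**Working it through.** **Inputs from the documents.** Target difference 0.5, attrition allowance 20%, 155 analysable and 193 recruited per condition (all Section 8.2). For the spread, "we assume the standard deviation of the food security score is 1.5". The scale runs from 0 to 6, higher being worse (Section 8.4.2). Alpha and sidedness are not stated; 0.05 is assumed.

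**Step 1: the plan's own figures.** With the normal formula n = 2 × (z_alpha + z_power)² × SD² / difference², 90% power needs 155 per condition at one-sided 0.05 and 190 at two-sided 0.05. The stated 155 therefore matches the one-sided calculation; sidedness is a separate matter. The inflation is 155 / 0.80 = 193.75, against 193 stated (193 × 0.80 = 154.4). The planned loss is 0.20 × 193 = 38.6 per condition, or 0.20 × 386 = 77.2 overall.

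**Step 2: bias formula.** Let d be the proportion lost in an arm and gap the mean score of those lost minus the mean of those retained. The mean of everyone enrolled in that arm is the retained mean + d × gap, so the respondents' mean is too low by d × gap. The between-arm contrast is off by

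shift = d_int × gap_int − d_ctrl × gap_ctrl.

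A positive shift flatters online ordering. If the gaps change sign, so does the shift.

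**Step 3: assumed scenarios.** The loss splits and gaps below are assumptions. SE = 1.5 × sqrt(1/n_int + 1/n_ctrl) on those retained; with 20% lost in each arm this is 1.5 × sqrt(2/154.4) = 0.171. The last two columns give the false-positive rate when there is no true effect, at nominal 0.05; the one-sided test is in the direction of the shift.

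| Loss int / ctrl | Gap int / ctrl | Shift (points) | Share of 0.5 | Two-sided | One-sided |
|---|---|---|---|---|---|
| 20% / 20% | 1.0 / 1.0 | 0.20 − 0.20 = 0 | 0% | 5.0% | 5.0% |
| 25% / 15% | 0.5 / 0.5 | 0.125 − 0.075 = 0.05 | 10% | 6.0% | 8.8% |
| 25% / 15% | 1.0 / 1.0 | 0.25 − 0.15 = 0.10 | 20% | 9.0% | 14.4% |
| 20% / 20% | 0.5 / 0 | 0.10 | 20% | 9.0% | 14.5% |
| 20% / 20% | 1.0 / 0 | 0.20 | 40% | 21.6% | 31.8% |
| 20% / 20% | 1.5 / 0 | 0.30 | 60% | 42.0% | 54.5% |

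Loss of 30% against 10% with a common gap of 0.5, 1.0 or 1.5 gives the same shifts of 0.10, 0.20 and 0.30.

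**Step 4: Aim 2.** Section 8.1 expects a larger benefit in younger adults. If older clients who do badly leave the intervention arm, the effect in the older group looks better than it is and the age difference shrinks, which works against that hypothesis. If the selective loss is among younger clients, the difference grows. The documents do not settle which.

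**The case against.** The strongest reply is that the primary outcome is not collected at the pantry or through the ordering platform. It is a phone survey in both arms (Section 6.1), backed by contact details, a booked appointment, reminders and payment. Someone who leaves the pantry can still give a food security score. This stands, and it weakens the route from online ordering to missing data. It does not close that route, because retention effort is not an analysis method and calling people who have left the pantry is not written down.

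Several stronger readings are tempting, and the documents do not support them:

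- *That online ordering causes loss.* Section 5.4 says the move happens regardless of study participation. It does not link the move to leaving the study. A smaller expected benefit in older adults is likewise not evidence that they drop out.
- *That one in five will be lost.* Section 8.2 calls 20% a potential rate; it is an allowance.
- *That the result is biased towards online ordering by 40% of the target.* That is one row of assumed inputs. A gap of 1.0 is 0.67 SD and 1.5 is a full SD, and no source in the documents supports either. Loss of people whose food security improved would push the other way.
- *That baseline scores exist for all 386.* Section 2.3.1 lets participants skip questions.

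It can also be said that Section 4.1 speaks of analysing baseline and follow-up data, and that adjustment for unbalanced characteristics could take in the baseline score. But the balance check concerns demographic characteristics, and the model in 8.4.2 contains neither baseline score nor period. Finally, a mixed model does not by itself repair loss driven by unobserved outcomes after the transition. That is correct, and it is why the shift analyses are needed.

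**Conclusion.** The point holds as an unresolved contradiction between 7.2 and 8.2, combined with a primary analysis that by default would use only follow-up respondents and discard their baseline scores. The consequence is conditional: bias arises only if loss relates to outcome differently in the two arms. Its size and direction cannot be determined from the documents. The scenarios run from nothing to 0.30 points, which is enough to matter against a 0.5-point target at the upper end and negligible at the lower. The Aim 2 interaction could be distorted either way. The change should be made because it is cheap and because the two-wave model also matches the change hypothesis in 8.1, not because a particular bias has been shown.

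**What to change.** 1. **Section 7.2:** replace the present entry with a definition of loss to follow-up and the steps taken to reach participants, consistent with the 20% allowance in 8.2.
2. **Section 8.3:** state that every enrolled participant is called in the follow-up window, whether or not they still use the pantry, and is analysed in the arm of the pantry where they were recruited.
3. **Section 8.4.2:** make the primary model a two-wave likelihood (mixed) model of the food security score with condition, period, condition × period and age group, using all available baseline scores. The condition × period term is the effect of interest. State that the model is valid if loss depends only on observed data.
4. **Sensitivity analysis:** shift the missing follow-up scores over a range such as 0.5 to 1.5 points, in either arm and in both directions, and report where the conclusion changes.
5. **Reporting:** give loss by arm and age group.

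The cost is revised wording and a little more analysis, with no additional participants or survey items. The model depends on the ID linkage in Section 9.6 working across the two surveys. Since Section 9.4 keeps personal identifiers apart from survey responses, the plan should say how the same ID is entered at both surveys.

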8.3 Populations for Analyses

The study population is a sample of adults aged ≥ 18 years.

8.4 Statistical Analyses

We will perform a linear regression to assess balance of demographic characteristics between conditions; because of the natural experiment design, these characteristics should be balanced. To assess differences in outcomes between study conditions, we will regress the outcome variable on indicator variables for the experimental conditions, with the control condition as the reference group; if necessary, we will also adjust for any respondent characteristics that may be unbalanced by condition. The design and methods proposed will achieve robust and unbiased results because random assignment to an intervention group or control group in the context of a natural experiment minimizes bias.

We will also test for potential interaction effects at the individual-level by adding an interaction term for age group (18-61 vs. ≥ 62 years). In the food pantry network, an average of 25% of clients served are above 61 years of age, so we will have adequate variation to assess potential interactions by age group. For assessing differences in the frequency of food pantry visits per month at the food pantry-level, we will also add an interaction term for age group, which the

food pantry network measures as child (<18 years), adult (18-61 years), and older adult (≥ 62 years).

